#### 4.10.4 Physical Examinations

Physical examination findings and number of participants are summarized as the count and percentage of participants by eCRF pre-defined categories at last visit. Results of Physical Examination will be included as a listing for each arm and overall.

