Both the interim and final analysis of the 48 week double-blind phase will use a mixed effects repeated measures model. The co-primary endpoints at the final analysis are both required to attain 5% significance level in order to be reported. If both co-primary outcomes are significant, then the remainder of the secondary outcomes will be tested at overall 5% significance level using a Holm step-down test. This will preserve alpha at 5% overall for all endpoints reported.

The primary analysis for the study will take place after all subjects have completed all visits in the double-blind phase.

Co-Primary Endpoints

The mean change in ADAS-Cog 11 from baseline to week 48 of the double-blind phase, compared between the BHV-4157 treatment group and the placebo group.

The mean change in CDR-Sum of Boxes from baseline to week 48 of the double-blind phase, compared between the BHV-4157 treatment group and the placebo group.

Secondary Endpoints	The change in the NPI total score from baseline to week 48 of the double-blind phase.
	The change in ADCS-ADL total score from baseline to week 48 of the double-blind phase.
	The change in MMSE from baseline to week 48 of the double-blind phase.
	The change in MRI Quarc bilateral hippocampal volume from screening to week 48 of the double-blind phase.
	The change in safety and tolerability measures including: (1) adverse events; (2) clinical laboratory tests; (3) vital signs; (4) physical examinations; (5) ECGs.
Exploratory Endpoints	Exploratory endpoints include: (1) the change in MoCA scores from baseline to week 48 of the double-blind phase; (2) the change in ADCOMS total score from baseline to week 48 of the double-blind phase; (3) the change in MRI Quarc bilateral lateral ventricles and whole brain volume from screening to week 48 of the double-blind phase; (4) the change in composite z score from baseline to week 48 of the double-blind phase on the cognitive composite outcome computed using measures from the NACC Neuropsychological Test Battery; (5) BHV-4157 and riluzole pharmacokinetics; (6) treatment response in participants by Apo E genotype; and (7) CSF, serum and plasma biomarker panel (Aβ42, Aβ42/40 ratio, total tau, p-tau-181, neurogranin, NfL, YKL-40, VILIP, SNAP-25, sTREM2, GFAP) will be assessed at screening, week 24, and week 48. CSF will be assessed in a subset of the study population (estimated n=50 active, n=50 placebo).

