2 STUDY DESIGN

This is a phase 2 multi-center, randomized, double blind, placebo-controlled, parallel group study in patients with mild to moderate Alzheimer's disease.

[figure not shown]
Participants will be randomized to one of two groups: 280 mg of BHV-4157 or placebo. The BHV-4157 treatment dose of 280 mg was selected for evaluation in the current study based on evidence summarized in Section 1.8. Double-blind treatment duration is approximately 48 weeks (12 months). There is a screening period of up to 42 days and a 4-week post-treatment observation period (for subjects who do not participate in the Open-Label Extension phase).

In addition, subjects who are completing or have completed the Double-blind treatment phase may be offered the opportunity to enroll in an Open-Label Extension phase, in which subjects will receive open-label treatment with BHV-4157 for approximately 48 weeks. Enrollment into the Open-Label Extension phase for all subjects is contingent on the PI's judgement that open-label treatment offers an acceptable risk-benefit profile for each individual. All subjects who enter the Open-Label Extension phase will need to sign a new informed consent form.

- Participants who are completing the double-blind treatment phase may directly enter the Open-Label Extension phase. These participants should not complete the follow-up safety visit at Week 52 (of the double-blind treatment phase). Instead, these participants should continue directly into the Open-Label Extension phase starting at Week 48 (of the double-blind treatment phase). The Week 48 visit will serve as the Baseline visit in the Open-Label Extension phase for participants who are going directly from the double-blind treatment phase to the OLE. Thereafter, participants will undergo visits at Week 4, Week 8, Week 12, and then every 12 weeks of the Open-Label Extension phase as outlined in Table 3 (Schedule of Assessments/Time & Events- Extension Phase).
- Participants who previously completed the double-blind treatment phase prior to the Open-Label Extension phase of the study being open for recruitment at their study center, may also enter the Open-Label Extension phase.

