8.1.10 Week 52 Safety Follow-up (± 7 days)

All participants returning for week 52 (who are not going into the Open-Label Extension phase) will undergo the following procedures after the Week 48 visit is completed in person:

- Physical exam
- Vital signs (sitting blood pressure, pulse, temperature, respiration rate)
- Weight
- Documentation of concomitant treatment
- Documentation of adverse events
- Blood samples for safety laboratory tests (hematology and serum chemistry, as listed in Section 8.2)
- Resting 12-lead ECG
- Sheehan Suicidality Tracking Scale

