8.4 Physical and Neurological Examination

A physical examination will be performed by a medically qualified professional at every study visit. A review of the major body systems will be performed and vital signs will be assessed. A neurological examination will only be performed at screening and will include assessment of motor strength, sensory, deep tendon, tremor, cerebellar, cranial, and mental status.

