12.7.5 Other Safety Parameters

Vital signs and ECG parameters are summarized across groups by visit using descriptive statistics, and at each outcome visit and at end of study.

Physical examination findings and number of participants are summarized as the count and percentage of participants by eCRF pre-defined categories at last visit. Concomitant medications are summarized by treatment group, drug class and preferred term. Vital signs are summarized by visit using descriptive statistics.

Overall interpretation results for ECGs and the Investigator interpretation results are collected as normal, abnormal not clinically significant, and abnormal clinically significant. Participants whose interpretation shifts from normal to abnormal are listed separately including description of the abnormality and any associated comments.

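### The physical examination table uses an undefined last visit with no baseline, pools on-drug and off-drug examinations, and cannot separate new from pre-existing findings (low severity)

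*SAP*

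**What the plan says.** SAP 4.10.4 has two sentences. The first sets the table: findings are "summarized as the count and percentage of participants by eCRF pre-defined categories at last visit". The second adds a listing: "Results of Physical Examination will be included as a listing for each arm and overall". The listing is not limited to any visit. Protocol 12.7.5 gives the same table rule: "Physical examination findings and number of participants are summarized as the count and percentage of participants by eCRF pre-defined categories at last visit". That section sits under the open-label extension heading, but 12.7.2 says safety is presented separately for the double-blind and extension phases.

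On the schedule, Protocol 8.4 says "A physical examination will be performed by a medically qualified professional at every study visit". Table 1 of Appendix I marks examinations at screening, baseline, Weeks 4, 8, 12, 24, 36 and 48, and Week 52. Week 52 is conditional: "All participants returning for week 52 (who are not going into the Open-Label Extension phase) will undergo the following procedures". For participants going straight into the extension, Protocol section 2 says "These participants should not complete the follow-up safety visit at Week 52".

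On the endpoint, the Secondary Endpoints row of the Protocol synopsis reads "The change in safety and tolerability measures including: (1) adverse events; (2) clinical laboratory tests; (3) vital signs; (4) physical examinations; (5) ECGs". Protocol 4.2.2 instead speaks of differences between the groups, and SAP 2.4.2 simply lists physical examinations among the safety measures.

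**The concern.** A count at one time point shows prevalence, not change. A heart murmur or abnormal gait present at baseline counts the same as one that arose on drug, although baseline examinations exist. The chosen time point also differs between participants: some are examined at the end of treatment and others about four weeks after it. A sign that appeared on drug and resolved before the last visit is absent from the table.

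At stake is whether the examination data, collected at every clinic visit of the double-blind phase, give a usable by-arm summary of new findings. No efficacy conclusion depends on it.

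**Working it through.** **1. Off-drug interval at Week 52.** The plan's own figure is a 4-week post-treatment observation period (Protocol section 2). Week 52 − Week 48 = 4 weeks = 28 days, which reproduces it.
- The return appointment is 4 weeks ± 7 days (Protocol 8.1.9): 28 − 7 = 21 to 28 + 7 = 35 days.
- If the ± 7-day windows of both visits vary independently: 28 − 14 = 14 to 28 + 14 = 42 days.
- Assumption: the last dose is taken at about the Week 48 visit.

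**2. Which examination is last in the double-blind phase.** The scheduled on-drug, post-baseline examinations are Weeks 4, 8, 12, 24, 36 and 48, six in all.

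| Participant | Last double-blind examination | On-drug examinations in the table |
|---|---|---|
| Completer with a Week 52 visit | Week 52, off drug | 0 of 6 |
| Direct extension entrant | Week 48 | 1 of 6 |
| Early terminator (no 4-week return appointment, Protocol 8.1.9) | Early Termination | at most the last one |

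Two further groups do not fit neatly. Participants who finished before the extension opened at their site may enter it later, and some may already have had a Week 52 examination. Participants who stop drug may continue visits (Protocol section 10), so their last examination can be long after the last dose.

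**3. Whether a general SAP rule settles the visit.**
- SAP 4.10 asks for separate summaries by phase, which favours reading the rule as last within phase. SAP 4.10.4 does not say so.
- The safety on-treatment period in SAP 4.4 runs to last dose + 30 days for those not entering the extension. Since 28 < 30, a nominal Week 52 examination is on-treatment by that definition and would still be chosen over Week 48. Only examinations at day 31 or later drop out.
- SAP Table 3 does not name physical examination. If its rule were borrowed, Week 52 is day 52 × 7 = 364, inside the Week 48 window of days 323–420, and the latest record in a window is used. Week 52 would again displace Week 48 (day 336).

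**4. Extension phase.** Table 3 of the Protocol appendix schedules examinations only at extension baseline and at extension Week 48 or Early Termination. The visit two weeks after the last dose has none, so the last visit read literally holds no scheduled examination.

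**5. Comparison with the other safety domains.** Vital signs get change from baseline by arm and visit (SAP 4.10.5). Laboratory data get shifts from baseline to worst on-treatment value (4.10.3). ECG gets by-visit statistics and QTcF change categories (4.10.6). Physical examination has no baseline reference at all.

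**The case against.** A reader might infer that on-drug findings go unreported. The documents do not support that. The listing in SAP 4.10.4 is unrestricted, so all six on-drug examinations fall within it. Protocol section 11 also defines an adverse event to include an unfavourable sign or a worsened pre-existing condition, and SAP 4.10.2 tabulates treatment-emergent events by arm whether or not they resolve. This stands, and it means the proposed table partly overlaps the adverse event tables. The overlap is incomplete: Protocol 8.6 and the visible text of 11.5 say when an abnormal ECG or laboratory result becomes an adverse event, while 8.4 gives no such rule for an examination finding.

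A reader might also infer a bias toward no difference. Some loss of sensitivity to reversible signs is plausible, but neither its direction overall nor its size can be derived from the documents. No test of examination findings is planned, and pre-existing findings should balance under 1:1 randomisation, adding noise and not favouring an arm.

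The word change appears for the double-blind phase only in the synopsis, where it also governs adverse events and may be loose drafting. A by-arm count does address the between-group wording of Protocol 4.2.2. That narrows the mismatch to the synopsis but does not make a last-visit count informative.

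Finally, the 30-day window also lets Week 52 vital signs and ECGs count as on-treatment, so the mixing is not peculiar to physical examination. That is fair, but those domains also have by-visit summaries and a baseline reference.

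**Conclusion.** The point holds in limited form. The only planned physical examination table rests on an undefined visit and has no baseline. In the double-blind phase, read as last within phase, it mixes end-of-treatment examinations with examinations nominally 28 days off drug. It cannot show change or separate new from old findings, and it leaves earlier on-drug examinations to a listing and to whatever was recorded as an adverse event. The zero-of-six figure applies to completers seen at Week 52, and one-of-six only to direct extension entrants. How many participants fall in each group cannot be computed, because the documents give no extension uptake.

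Severity is low. This is descriptive safety reporting with two partial backstops.

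**What to change.** In SAP 4.10.4, replace or supplement the last-visit count with the number and percentage of participants, by arm and phase, who have a new or worsened finding against that phase's baseline (SAP 4.3.1.2 already defines baseline by phase). Tabulate by eCRF body-system category, over all post-baseline examinations up to and including Week 48 or Early Termination of the phase.

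Exclude Week 52 by name. Limiting the table to on-treatment data is not enough, because the last dose + 30 days window can include it. Show Week 52 in a separate off-drug follow-up table. State how examinations are handled for participants who stop drug but keep attending. Align Protocol 12.7.5.

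This assumes that the eCRF categories are body systems recorded in enough detail to judge worsening. If they hold only normal or abnormal, count shifts from normal to abnormal.

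The cost is one re-specified descriptive table and a short follow-up table, from data already collected. No visit, procedure or clinical rule changes.

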#### 4.10.5 Vital Signs and Physical Measurements

The observed value and change from baseline in vital signs and physical measurements will be summarized for each arm at each visit for the Randomization and Extension Phases, separately. The summary will be based on the "on-treatment" data after the date/time of first dose of study drug and within 30 days after the last dose of study drug (see section 4.3 for detailed definition of "on-treatment").

In addition, the number and percentage of participants with at least one post-treatment vital sign measurement meeting any of these criteria will be summarized:

- Systolic Blood Pressure: <90 mmHg, >140 mmHg, >160 mmHg
- Diastolic Blood Pressure: <50 mmHg, >90 mmHg, >100 mmHg
- Pulse Rate: <60 bpm, >100 bpm
- Body Weight: decrease of  $\geq$ 7% from baseline and increase of  $\geq$ 7% from baseline
- Temperature: >38.0 °C, <36.0 °C

The number and percent of subjects meeting these criteria will be summarized for the Randomization and Extension Phase, separately as well as the overall BHV-4157 treated exposure. A subject listing will provide for each vital sign measure abnormality criteria listing any subject meeting the criteria with a complete list of all of their values that particular vital sign measure with the specific assessments that meet the criteria indicated.

The criteria summarized for the Randomization Phase will also be repeated for Treated subjects completing (or discontinuing) double-blind treatment prior to versus on or after start of COVID-19 pandemic crisis (March 13, 2020).

#### 4.10.6 Electrocardiogram

Descriptive statistics for ECG interval data (e.g., QRS, PR, QT, QTcF), and ventricular heart rate will also be reported by visit for the Randomization and Extension Phases, separately. The summary will be based on the data after the date/time of first dose of study drug and within 30 days after the last dose of study drug (see section 4.3 for detailed definition of "on-treatment").

In addition, the number and percentages of subjects with at least one post-treatment QTcF > 450 ms, >480 ms, and >500 ms will be summarized for the Randomization and Extension Phase, separately, as well as the overall BHV-4157 treated exposure. Similar number and percentages will be presented for subjects with at least one post-baseline QTcF Change from baseline >= 30 ms to < 60ms and those with at least one change from baseline >= 60 ms. A subject listing will provide each QTcF sign measure, specifying any subject meeting the criteria with a complete list of their QTcF assessments with the ones meeting the criteria indicated.

The criteria summarized for the Randomization Phase will also be repeated for Treated subjects completing (or discontinuing) double-blind treatment prior to versus on or after start of COVID-19 pandemic crisis (March 13, 2020).

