- 8. Brain MRI at screening shows evidence of infection, tumor, cortical infarction, extensive white matter disease (Fazekas score > 2), or multiple lacunes in prefrontal or critical memory regions; inconclusive findings may be subject to review by the ADCS Imaging Core.
- History of a major depressive episode within the past 6 months of screening.
- History of schizophrenia diagnosis.
- History of bipolar disorder.
- History of seizures within 2 years of screening.
- History of alcohol abuse or dependence or drug abuse in the past 5 years.
- Insulin-dependent diabetes or uncontrolled diabetes with HbA1c value >8.0 %.
- Hepatitis B, C, or HIV infection.
- Clinically significant laboratory abnormalities that may influence study assessments as determined by the investigator.
- Untreated or insufficiently treated hypothyroidism, vitamin B12 or folate deficiency.
- 18. ECG obtained during screening that, in the opinion of the investigator, is clinically significant with regard to the participant's participation in the study. Corrected QT interval (QTcF) must be evaluated using Fridericia's formula, and must not exceed 480 msec.
- 19. Cancer or a malignant tumor within the past 3 years, except patients who underwent potentially curative therapy with no evidence of recurrence for >3 years. Patients with stable prostate cancer or non-melanoma skin cancers are not excluded.

- 20. Participation in another clinical trial for an investigational agent and having taken at least one dose of study medication, unless confirmed as having been on placebo, within 12 weeks prior to screening. The end of a previous investigational trial is defined as the date of the last dose of an investigational agent.
- Having received riluzole for more than 4 weeks prior to screening or with known tolerability difficulties to riluzole.

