#### 4.10.9 Subjects Identified for Narratives

A safety narrative will be prepared for each subject who received at least one dose of troriluzole and experienced the following events (regardless of relationship to study drug) on-treatment with Troriluzole:

- All deaths on-treatment and post-treatment through the end of the study
- SAEs on-treatment, which includes up to 30 days after the last dose of study drug; SAEs that occur > 30 days (i.e., during the follow-up period) will be included per the clinical judgment of the Biohaven medical monitor
- All premature discontinuations of study drug due to AEs (either identified through "action taken" or "end of treatment status")
- The following on-treatment events of special interest:
  - Neutropenia based on laboratory results and defined as minimum absolute neutrophil count < 500 per mm3

  - LFT abnormalities:
    - $\circ \quad \text{ALT or AST} > 3x \text{ ULN}$
    - ALT or AST > 3x ULN, and serum total bilirubin > 2x ULN

Interstitial lung disease Standardized MedDRA Query (SMQ) including eosinophilic pneumonia and hypersensitivity pneumonitis

These select events are described in the current version (v3) of the Biohaven Safety Narrative Scope for BHV-4157 (troriluzole). Because select events may be subject to change, updates to the list of events or selection algorithms after database lock may be described in a Note to File (NTF) rather than amending the SAP.

A by-subject listing of safety narrative subject identifiers will be presented for all troriluzole treated subjects with the select events as described above.

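### The categorical QTcF, blood pressure, pulse and temperature counts ignore the baseline value, so they mix pre-existing with new abnormalities; a not-met-at-baseline row would separate them

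*SAP*

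**What the plan says.** For ECGs, SAP 4.10.6 plans that "the number and percentages of subjects with at least one post-treatment QTcF > 450 ms, >480 ms, and >500 ms will be summarized". This covers the Randomization Phase, the Extension Phase and the overall BHV-4157 exposure. It then adds counts for "at least one post-baseline QTcF Change from baseline >= 30 ms to < 60ms" and for changes of 60 ms or more, and a listing of all QTcF values for participants who meet a criterion.

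For vital signs, SAP 4.10.5 first summarises observed values and changes from baseline by arm and visit. It then says that "participants with at least one post-treatment vital sign measurement meeting any of these criteria will be summarized". Examples are "Systolic Blood Pressure: <90 mmHg, >140 mmHg, >160 mmHg" and "Pulse Rate: <60 bpm, >100 bpm"; diastolic pressure (>90 mmHg) and temperature (<36.0 °C) have similar fixed limits. Only the weight criteria (±7%) refer to baseline.

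On entry, Protocol 7.2 (criterion 18) says: "Corrected QT interval (QTcF) must be evaluated using Fridericia's formula, and must not exceed 480 msec". The eligibility criteria give no numeric limit for blood pressure, pulse or temperature; serious or unstable illness is excluded on judgement.

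Other safety data are handled with reference to baseline. SAP 4.10.2 counts adverse events that began or worsened after first dose, and SAP 4.10.3 plans baseline-to-worst shift tables for laboratory tests, including the liver tests.

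**The concern.** A participant who enters with QTcF 470 ms and stays there counts as a >450 ms case. One who enters with systolic pressure 150 mmHg and stays there counts as >140 mmHg. Neither has changed. The QTcF >450 ms cut-off lies inside the permitted entry range and >480 ms lies at its limit. The blood pressure, pulse and temperature cut-offs have no entry limit to be compared with.

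In the double-blind phase the placebo arm carries the same background, so any relative difference between arms is flattened but not biased. The Extension Phase and pooled BHV-4157 tables have no concurrent arm to show the background, and a reader cannot tell from the percentage how much of it was there before treatment.

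The wording adds a smaller problem. Both counts say 'post-treatment', while SAP 4.10.9 sets that term against 'on-treatment' ("All deaths on-treatment and post-treatment through the end of the study"). Both sections also cite 4.3 for the on-treatment definition, which is in 4.4.

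**Working it through.** The documents give no expected flag rate and no distribution for QTcF or vital signs, so there is no planned figure to reproduce. The size below rests on assumptions.

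**Inputs from the documents.** Cut-offs: SAP 4.10.5 and 4.10.6. QTcF entry limit 480 ms: Protocol 7.2. Visits after baseline (Protocol Appendix I, Table 1): ECG at weeks 12, 24, 48 and 52, so k = 4; vital signs at weeks 4, 8, 12, 24, 36, 48 and 52, so k = 7. These are maxima, because those entering the extension skip week 52. Planned 168 per arm: Protocol 12.1.1.

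**Assumptions, not in the plan.** QTcF mean 410, 420 or 430 ms with SD between/within persons 15/8, 20/10 or 20/15. Systolic pressure mean 125, 132 or 138 mmHg, SD 13/9. Pulse mean 66, 70 or 74 bpm, SD 8/5. Normal distributions, no drug effect. The central QTcF case is mean 420, SD 20/10.

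**Formulas.** Let m be a person's true mean and p(m) the probability that one reading is not past the limit (for an upper limit c, p = Φ((c − m)/SD within)).

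- Any reading past the limit: A = E[1 − p^k].
- The same, and baseline not past the limit: B = E[p(1 − p^k)].
- For QTcF, both are taken among those with baseline ≤480 ms.

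A and B were obtained by simulation, 1,000,000 participants per scenario.

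**Hand check of the share past the limit at baseline.**

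- Systolic, mean 125: 1 − Φ(15/√(13² + 9²)) = 1 − Φ(0.949) = 17.1%.
- Pulse, mean 70: Φ(−10/√(8² + 5²)) = Φ(−1.06) = 14.5%.
- QTcF, mean 420, total SD √(20² + 10²) = 22.36: 9.0% exceed 450 and 0.36% exceed 480, so (9.0 − 0.36)/(100 − 0.36) = 8.7% after the entry limit.

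**Results with no drug effect.** Percentages are of all participants, except the last column, which is (A − B)/A.

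| Criterion | Mean | Past limit at baseline | A | B | Flags already past limit at baseline |
|---|---|---|---|---|---|
| QTcF >450 | 420 | 8.7% | 17.3% | 10.2% | 41% |
| Systolic >140 | 125 | 17.1% | 41.8% | 26.5% | 37% |
| Systolic >140 | 132 | 30.6% | 61.5% | 32.6% | 47% |
| Systolic >140 | 138 | 44.9% | 76.2% | 32.8% | 57% |
| Pulse <60 | 66 | 26.2% | 53.4% | 28.9% | 46% |
| Pulse <60 | 70 | 14.5% | 35.2% | 22.3% | 37% |
| Pulse <60 | 74 | 6.8% | 19.9% | 14.1% | 29% |

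For central QTcF, 0.173 × 168 ≈ 29 flagged per arm becomes 0.102 × 168 ≈ 17. Over all nine QTcF scenarios A is 2.4-40.5% and B is 1.8-24.7%. For >480 and >500 ms, A = B in the randomised phase, because nobody may enter above 480 ms. Diastolic pressure and temperature were not simulated.

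**Dilution.** QTcF >450 with mean 430, SD 20/10 and an assumed +10 ms: all-comers 31.5% against 49.8%, ratio 1.58; not met at baseline 16.2% against 32.8%, ratio 2.02. Systolic >140 with mean 132 and +3 mmHg: 61.5% against 69.3%, ratio 1.13; then 32.6% against 39.6%, ratio 1.21. The absolute differences hardly move (18.3 and 16.6 points; 7.8 and 7.0 points), so the loss is in relative contrast.

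**The case against.** The strongest reply is that the plan already relates these data to baseline. The QTcF change categories sit beside the absolute counts, and the participant who stays at 470 ms falls in neither of them. Vital-sign changes are summarised by arm and visit, weight is baseline-relative, flagged participants are listed with all their values, and Protocol 12.7.5 lists ECG interpretations that move from normal to abnormal. All-comers counts next to baseline-related ones are also the SAP's pattern for laboratory grades.

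Much of this stands, and it makes the point a modest one. But by-visit mean changes do not give the number of people who newly crossed a limit, a listing leaves that count to the reader, and the ECG shift listing uses the investigator's interpretation rather than QTcF categories. In the extension, baseline is reset to a value near the first extension dose, which for those continuing BHV-4157 can be an on-drug value. SAP 4.10.6 names no baseline for the pooled exposure.

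Three stronger readings are tempting and not supported:

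- **Most flags would occur without any drug effect.** The documents cannot show this. If the background share is taken as placebo rate over active rate, the assumptions give 83-93% for systolic >140 (+3 mmHg) and 74-85% for pulse <60 (−2 bpm). For QTcF >450 it is 50-82% at +5 ms but 10-54% at +20 ms. For >480 and >500 ms it is below half in every scenario with a shift of 10 ms or more.
- **All the QTcF cut-offs lie within the entry range.** The >500 ms cut-off is 20 ms above the limit ("must not exceed 480 msec").
- **'Post-treatment' restricts the counts to values after drug is stopped, so the extension QTcF count must be zero.** The sentence before each count sets the window from first dose to 30 days after last dose. An early-termination or unscheduled ECG could also follow the last dose. The term is loose and needs clarifying, no more.

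A baseline condition also adds no confirmation rule and cannot supply a missing control arm. Flags from visit-to-visit variation remain, as column B shows.

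**Conclusion.** The point holds as a low-cost improvement to descriptive safety tables. The absolute QTcF counts and the blood pressure, pulse and temperature counts combine abnormalities present at entry with new ones, and for the three vital signs no planned table separates them. That follows from the text alone.

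The size does not. Under the assumed distributions and no drug effect, the baseline condition removes roughly 30-55% of systolic and pulse flags and about 40% of central-case QTcF >450 flags. It removes none of the >480 or >500 ms flags in the randomised phase. Different means or variability would move these figures.

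The consequence is reduced relative contrast between arms in the double-blind phase, and percentages that are hard to interpret in the extension and pooled tables. No efficacy conclusion is affected.

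**What to change.** In SAP 4.10.5 and 4.10.6:

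1. Keep the all-comers counts. For QTcF, blood pressure, pulse and temperature, add a row for participants who met the criterion on treatment and did not meet it at baseline, or a baseline-by-worst-value shift table as planned for the liver tests. For QTcF the shift table is more informative, because it separates those who reach >480 ms from 450-480 ms from those who started at or below 450 ms.
2. State the denominator. The figures above use all participants. Restricting it to those not past the limit at baseline gives 10.2/(100 − 8.7) = 11.2% for central QTcF >450 rather than 10.2%.
3. For the pooled BHV-4157 tables, define baseline as the last value before the first BHV-4157 dose, so that it is never an on-drug value.
4. Replace 'post-treatment' with 'on-treatment (Section 4.4)' in both sections, and correct the cross-references to 4.3.

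The cost is a SAP wording change and one extra condition in the table programs. All the data are already collected.
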